### 7.3.2. Reasons for Discontinuation from the Clinical Study

Reasons for discontinuation from the study include:

- Patient withdraws consent for continued participation
- Lost to follow-up
- Death of the patient
- The Sponsor deems it necessary to discontinue the study

Withdrawal of full consent for a study means that the patient does not wish to receive further investigational treatment and does not wish to or is unable to continue further study participation. Any patient may withdraw full consent to participate in the study at any time during the study. The investigator will discuss with the patient the most appropriate way to withdraw to ensure the patient's health.

No patients will be replaced during the dose-expansion part of the clinical study. Patients are free to withdraw from the study at any time without providing reason(s) for withdrawal and without prejudice to further treatment.

Patients withdrawing from the study will be requested to complete the same final evaluations as patients completing the study according to this protocol, particularly safety evaluations. The aim is to record data in the same way as for patients who complete the study.

Reasonable efforts will be made to contact patients who are lost to follow-up. These efforts must be documented in the patient's file.

The Sponsor has the right to terminate the study at any time. In this event, the investigator(s) will be informed of the reason for study termination.

## 8. TREATMENT OF PATIENTS

### 8.1. Description of Study Drugs

#### 8.1.1. DSP-7888 Dosing Emulsion Investigational Product

DSP-7888 Dosing Emulsion, also known as Adegramotide/Nelatimotide (INN) and Ombipepimut-S (USAN), is a synthetic peptide vaccine that consists of 2 synthetic peptide constructs: Nelatimotide (INN) (DSP-7888-K [killer peptide; an MHC Class I peptide]) and Adegramotide (INN) (DSP-7888-H [helper peptide; an MHC Class II peptide]). Both constructs are derived from the WT1 protein. DSP-7888 Dosing Emulsion, consisting of DSP-7888 in suspension with montanide 51 VG (labeled as DSP-7888-M), will be administered at the study site by staff trained in the administration of intradermal drugs.

#### 8.1.2. Nivolumab

Binding of the PD-1 ligands, PD-L1 and PD-L2, to the PD-1 receptor found on T cells inhibits T cell proliferation and cytokine production. Upregulation of PD-1 ligands occurs in some tumors and signaling through this pathway can contribute to inhibition of active T-cell immune surveillance of tumors. Nivolumab is a human immunoglobulin G4 monoclonal antibody that binds to the PD-1 receptor and blocks its interaction with PD-L1 and PD-L2, releasing PD-1 pathway-mediated inhibition of the immune response, including the antitumor immune response. Nivolumab will be administered at 240 mg every 2 weeks, as per the approved label.

On the days when both DSP-7888 Dosing Emulsion and nivolumab are administered, DSP-7888 Dosing Emulsion should be administered first. Nivolumab will be obtained by the clinical site.

#### 8.1.3. Pembrolizumab

Pembrolizumab is a monoclonal antibody that binds to the PD-1 receptor and blocks interaction with its ligands, PD-L1 and PD-L2. This binding results in the activation of T-cell-mediated immune responses against tumor cells. Blocking PD-1 activity has resulted in decreased tumor growth in genetically identical mouse tumor models. Pembrolizumab will be administered at a dose of 200 mg/8 mL IV over 30 ( $\pm$ 5) minutes every 21 days (3 weeks). On the days when both DSP-7888 Dosing Emulsion and pembrolizumab are administered, DSP-7888 Dosing Emulsion should be administered first. Pembrolizumab may be obtained by the clinical site in Phase 1b of the study. For Phase 2 of the study, pembrolizumab will be provided by [REDACTED]

### 8.2. Treatment Dose and Schedule (Phase 1 and Phase 2)

Treatment dosing and treatment schedules for DSP-7888 Dosing Emulsion, nivolumab, and pembrolizumab are provided in [Table 10](#).

**Table 10: DSP-7888 Dosing Emulsion, Nivolumab, and Pembrolizumab Treatment Dose and Schedule**

DSP-7888 Dosing Emulsion					Treatment Schedule DSP-7888 Dosing Emulsion, Nivolumab, Pembrolizumab	
Dose Level	Dose Intensity	Number of Injection* Sites	Amount Per Injection* Site (mL)	Total Amount to Administer Per Dosing Day (mL)	Nivolumab Arm (Arm 1)	Pembrolizumab Arm (Arm 2) of Phase 1b and Phase 2
DSP-7888 Dosing Emulsion Dose Level I	10.5 mg	6	0.1	0.6	
DSP-7888 Dosing Emulsion  induction phase: weekly for 4 weeks                      then  maintenance phase:                      every 2 weeks
 
nivolumab  240 mg                      administered IV                      over 30 (±5) minutes                      every                      14 days (2 weeks) in only                      maintenance phase
	
DSP-7888 Dosing Emulsion  induction phase: weekly for 3 weeks                      then  maintenance phase:                      every 3 weeks
 
pembrolizumab  200 mg/8mL administered IV                      over 30 (±5) minutes                      every                      21 days (3 weeks) in only                      maintenance phase

DSP-7888 Dosing Emulsion Dose Level II	3.5 mg	2	0.1	0.2		
DSP-7888 Dosing Emulsion Dose Level III (only used for dose reduction)	1.75 mg	1	0.1	0.1		

Abbreviations: IV = intravenous(ly)

### **8.3. Dose Modification**

Any study treatment may be interrupted at any time for any grade toxicity considered intolerable by the patient, based on the investigator's and patient's judgment.

In the case of any patient who has missed 4 or more consecutive doses of either study drug, that study drug should be permanently discontinued, but the patient may continue on the other nonmissed study drug. If the patient is experiencing clinical benefit and, in the opinion of the investigator it is in the patient's best interest to remain on study, the patient may continue treatment on a case-by-case basis, after documented discussion with the Sponsor.

Dose modification by treatment is described in the following sections.

#### **8.3.1. DSP-7888 Dosing Emulsion Dose Modification in Phase 1b**

The dose of DSP-7888 Dosing Emulsion should be held for any Grade 3 or Grade 4 toxicity that is related to DSP-7888 Dosing Emulsion and that is present on a scheduled dosing day. Dosing may be resumed at a reduced dose once the toxicity has resolved to Grade 1 or less. If the toxicity occurs at a dose of 10.5 mg, dosing may resume at the dosage of 3.5 mg. If the toxicity occurs at a dose of 3.5 mg, dosing may resume at a dose of 1.75 mg. No inpatient dose reduction is allowed during the DLT evaluation period.

On days when DSP-7888 Dosing Emulsion is held for toxicity, nivolumab (Arm 1) or pembrolizumab (Arm 2) should be administered if scheduled for that day. If toxicities related to DSP-7888 Dosing Emulsion preclude administration of DSP-7888 Dosing Emulsion for 4 consecutive treatments, DSP-7888 Dosing Emulsion should be discontinued; and the medical monitor and Sponsor should be consulted for case review and possible approval of continuing therapy with nivolumab (Arm 1) or pembrolizumab (Arm 2) alone.

After the induction phase, dose reduction is permitted due to ISRs if the investigator or subinvestigator has judged that a dose reduction is medically required.

Patients who experience Grade 3 or higher toxicities with a DSP-7888 Dosing Emulsion dose of 1.75 mg will be removed from the study.

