##### **Immune-related**

- Grade 3 or higher CTCAE v. 4.03 immune system disorder-related adverse reactions that persist as Grade 3 for >14 days, despite appropriate treatment, except for allergic reactions and autoimmune reaction
- Any Grade 3 or higher allergic reaction

- Any Grade 2 or higher autoimmune reaction with the following exceptions:
  - Grade 2 elevation of transaminases/hepatitis that recovers to Grade 0 or 1 within 10 days (for patients with liver metastases, elevation of transaminases due to hepatitis that recovers to baseline within 10 days)
  - Grade 2 hypothyroidism that recovers to Grade 0 or 1 within 7 days without steroids
  - Grade 2 diarrhea/colitis that spontaneously recovers to Grade 0 or 1 within 7 days with supportive care but without steroids
  - Grade 2 immune-related rash/dermatitis
- Any treatment-related Grade 4 ISR or Grade 3 ISR that requires hospitalization.

Any patient who experiences a DLT should be permanently removed from study treatment and should not be replaced.

Note that DSP-7888 Dosing Emulsion dosing has been managed with dose interruptions and/or adjustments for ISRs/AEs. Therefore, a DSP-7888 Dosing Emulsion dose interruption/delay for an AE related to an ISR that does not meet a DLT definition, as described above, will be considered a non-DLT modification. Non-DLT dose modifications will not be considered in determining the recommended dose for DSP-7888 Dosing Emulsion; however, they will be considered in determining further management of the DSP-7888 Dosing Emulsion dosing schedule in the expansion part, in combination with the selected PD-1 inhibitor.

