##### **8.3.2.1. Dose Reduction**

After the induction phase, dose reduction to 3.5 mg and subsequently to 1.75 mg is permitted due to ISR if the investigator considers that a dose reduction is medically required. No further dose reductions from 1.75 mg will be allowed. Re-escalation of the dose after dose reduction is not permitted.

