##### **8.3.2.2. Dose Interruption**

DSP-7888 Dosing Emulsion must be interrupted for any CTCAE (v.4.03) Grade 3 or 4 AE that the investigator considers to be related to DSP-7888 Dosing Emulsion. If toxicity is resolved to Grade 1 or less/baseline, the patient may restart treatment with DSP-7888 Dosing Emulsion but with a dose level reduction.

EXCEPTION: Because more serious ISRs (eg, Grade 3) may take longer to resolve due to the tissue injury, resolution to Grade 2 only is required for restart of treatment with DSP-7888 Dosing Emulsion. However, no dose reduction is required for following cases:

- Grade 3 or 4 hematologic laboratory abnormality which resolves to Grade 1 or less within 7 days without supportive care (blood transfusion or G-CSF agents)
- Grade 3 or 4 non-hematologic laboratory abnormality which resolves to Grade 1 or less within 7 days
- Grade 3 ISR that does not require hospitalization; patients may continue on the study treatment per investigator's judgment
- Grade 3 fatigue, fever, malaise, edema per CTCAE (v.4.03), which resolves to Grade 1 or less within 5 days, with appropriate supportive care
- Grade 3 nausea, vomiting, diarrhea per CTCAE (v.4.03), which resolves within 3 days, with appropriate supportive care

Before discontinuation of dosing for any of the above reasons, a conversation with the Medical Monitor may be applicable.

If toxicity is not resolved to Grade 1 or less (or Grade 2 or less in the case of ISRs, as described above) within 4 consecutive missing doses and, in the opinion of the investigator, the patient is clinically stable and receiving benefit from study drug, the patient may restart treatment with DSP-7888 Dosing Emulsion at a reduced dose on a case-by-case basis, only after consultation with the Sponsor.

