### 8.3.5.3. Management Guidelines for Grade 2/3 Injection Site Reactions

- Irrigation with physiologic saline and use of topical steroids, as described for Grade 1 ISRs above, should be instituted. If topical steroids are not sufficient for ISRs, local (subcutaneous) injection of steroids may be considered
- Topical antibiotics should not be used unless cultures indicate infection
- Open areas may be protected with a non-stick dressing
- Patients with Grade 3 ISRs that do not require hospitalization may remain on study and receive full dose per investigator's judgment
- If an abscess forms, incision and drainage should be carried out to avoid exacerbation of the inflammatory response around the site. After the drainage, the site should be washed with physiologic saline followed by application of topical steroids, as appropriate. Most abscesses should be sterile, but cultures should be obtained (see [Section 8.3.5.2](#) for recommendations for when the culture is positive)

- Emergency measures should be implemented for ISRs > Grade 3

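### For a Phase 1b Grade 3 injection site reaction not needing hospitalization, Protocol 8.3.1 requires a hold and a lower dose (study removal at 1.75 mg) while 8.3.5.3 allows full dose; the Phase 2 rules have narrower gaps

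*Protocol*

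**What the plan says.** **Phase 1b (Protocol 8.3.1).** "The dose of DSP-7888 Dosing Emulsion should be held for any Grade 3 or Grade 4 toxicity that is related to DSP-7888 Dosing Emulsion", if it is present on a scheduled dosing day. On resumption: "Dosing may be resumed at a reduced dose once the toxicity has resolved to Grade 1 or less". The steps are 10.5 to 3.5 mg and 3.5 to 1.75 mg. At the lowest level, "Patients who experience Grade 3 or higher toxicities with a DSP-7888 Dosing Emulsion dose of 1.75 mg will be removed from the study". The section has no exception for ISRs. It adds that, after induction, a reduction for ISRs is permitted if the investigator judges it medically required.

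**ISR management (Protocol 8.3.5.3).** "Patients with Grade 3 ISRs that do not require hospitalization may remain on study and receive full dose per" the investigator's judgment. The sentence is not restricted to a phase or a dose level.

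**Phase 2 (Protocol 8.3.2.1 and 8.3.2.2).** Section 8.3.2.2 requires interruption for any related Grade 3 or 4 event, after which "the patient may restart treatment with DSP-7888 Dosing Emulsion but with a dose level reduction". It then lists cases that need no reduction. One is a Grade 3 ISR without hospitalization, for which treatment may go on at the investigator's judgment. Section 8.3.2.1 says "After the induction phase, dose reduction to 3.5 mg and subsequently to 1.75 mg is permitted due to ISR" if medically required, and allows nothing below 1.75 mg.

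**Leaving treatment or the study (Protocol 7.3.1 and 7.3.2).** Patients who stop the product for any reason should carry on with study observations. Toxicity is not among the listed reasons for leaving the study.

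**The concern.** A site treating a Phase 1b patient with an outpatient Grade 3 ISR finds two sections that apply, and they lead to different doses. Phase 2 writes the ISR exception into its own dose-modification section and Phase 1b does not. A careful reader could therefore conclude that Phase 1b has no exception, while another could rely on 8.3.5.3.

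This affects the analysis because dose interruption, reduction and dose intensity are Phase 1b primary endpoints. SAP 5.2.6 counts patients with a reduction or interruption, SAP 5.2.6.1 computes relative dose intensity (RDI), and SAP 5.4.1 tabulates events leading to each action. SAP 5 limits the final CSR to safety, so these outputs are a large part of what will be reported. If sites followed different sections, the counts would partly reflect which section was read rather than how the product was tolerated.

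**Working it through.** No sample size or error rate is involved, so the check sets the rules side by side for a DSP-7888-related Grade 3 event.

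| Situation | First rule | Second rule | Result |
|---|---|---|---|
| Phase 1b, ISR without hospitalization, at 10.5 or 3.5 mg | 8.3.1: hold if present on a dosing day; resume one level lower at Grade 1 or less | 8.3.5.3: stay on study, full dose at the investigator's judgment | Contradiction |
| Phase 1b, same ISR, at 1.75 mg | 8.3.1: removed from the study | 8.3.5.3: may stay on study | Contradiction |
| Phase 1b, other toxicity outside the dose-limiting toxicity (DLT) window | 8.3.1: one path per dose level | None | Consistent |
| Phase 2, ISR without hospitalization | 8.3.2.2: interrupt | 8.3.2.2 exception: treatment may go on; 8.3.5.3: full dose | Dose level agrees; interruption unclear |
| Phase 2, related Grade 3 event outside the exceptions | 8.3.2.2: restart at a lower level | 8.3.2.1: describes reduction for ISR, after induction | Scope unclear |
| Phase 2, same event, already at 1.75 mg | 8.3.2.2: restart at a lower level | 8.3.2.1: no lower level allowed | Restart rule cannot be carried out |

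**Size for one event at 10.5 mg in Phase 1b.** Inputs are from Protocol Table 10: 10.5 mg is 6 injection sites and 3.5 mg is 2.
- Dose per site: 10.5/6 = 1.75 mg and 3.5/2 = 1.75 mg, so the dose difference is a difference in the number of sites.
- Next dose under 8.3.5.3: 10.5 mg at 6 sites. Next dose under 8.3.1: 3.5 mg at 2 sites, after a hold.
- Ratio: 3.5/10.5 = 33% of the 10.5 mg plan, for doses given after the reduction.
- Counts: 0 interruptions and 0 reductions under 8.3.5.3; 1 of each under 8.3.1.

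**Why 33% is not the overall RDI.** SAP 5.2.6.1 divides the sum of all administered doses by the sum of all planned doses over the intended treatment duration. Full doses before the event, held doses and reduced doses all enter. The result depends on when the event occurs and how long treatment lasts, which the documents do not give.

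**Study removal.** At 1.75 mg, 8.3.1 read literally ends study participation. Section 7.3.1 keeps patients who stop the product under observation, 7.3.2 lists no toxicity reason for leaving, and 8.3.1 itself foresees possible continuation of the PD-1 inhibitor alone after DSP-7888 is discontinued for toxicity. The text does not say whether study treatment or the study is meant.

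**The case against.** The best defence is that 8.3.5.3 is the specific rule for ISRs and 8.3.1 the general one, so the specific rule prevails. It can be added that both sentences are permissive, that 8.3.5.1 asks for judgment beyond the appearance of the lesion when grading, and that a reaction no longer present on a dosing day triggers no hold. The last point is correct and limits the finding to reactions present on a dosing day. The others do not settle it. No precedence is stated. The hold in 8.3.1 is an instruction, and its only resumption path is a lower dose. Grading judgment does not help once the reaction has been graded 3. The discretionary ISR sentence in 8.3.1 permits a reduction after induction but does not lift the hold.

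A reader might infer more than the documents support:
- **That one patient could be reduced, continued or removed, in either phase.** No patient faces all three. Study removal appears only in 8.3.1 at 1.75 mg, where no lower level exists. In Phase 2, full dose for an outpatient Grade 3 ISR is a written exception that agrees with 8.3.5.3.
- **That reductions are allowed only after induction, or only for ISR.** Neither 8.3.1 nor 8.3.2.1 contains that restriction. Both can be read as an added permission beside the grade-driven rule, so the fault is unclear scope.
- **That the DLT rule clashes with hold-and-reduce.** "Any patient who experiences a DLT should be permanently removed from study treatment and should not be replaced" concerns study treatment in the dose-search part, which is completed. Section 8.3.1 can be read as covering Grade 3 events that are not DLTs, and "No inpatient dose reduction is allowed during the DLT evaluation period" does not contradict taking DLT patients off treatment.
- **That survival and tumour follow-up would be lost.** This follows only from a literal reading of one sentence that 7.3.1 and 7.3.2 contradict, and SAP 5.5 drops efficacy analyses from the final CSR.
- **That the most common toxicity is affected.** The Protocol calls ISR of any grade the most common adverse event; it gives no Grade 3 frequency.

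**Conclusion.** The contradiction between 8.3.1 and 8.3.5.3 holds for a Phase 1b patient, enrichment cohort included, who has a related Grade 3 ISR that needs no hospitalization and is present on a dosing day. It applies at every dose level: hold and reduce against full dose at 10.5 and 3.5 mg, study removal against staying on study at 1.75 mg. The study-removal wording also conflicts with 7.3.1 and 7.3.2.

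Per event at 10.5 mg, the difference is a three-fold next dose, one interruption and one reduction. The total effect on the primary endpoints is unknown without the number and timing of such reactions. The per-event figures assume that a site follows one section throughout and that the 10.5 mg schedule is the planned dose.

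Phase 2 has three smaller defects: interrupt or continue for the same ISR, differing scope of reduction between 8.3.2.1 and 8.3.2.2, and a restart rule that cannot be carried out at 1.75 mg. The SAP reports Phase 2 as terminated, which limits the practical value of amending those rules. The documents do not say whether anyone remains on treatment. The text should be reconciled; nothing here says which dosing rule is right.

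**What to change.** - Reconcile 8.3.1 with 8.3.5.3, and 8.3.2.1 with 8.3.2.2, so that each event type and current dose level, including 1.75 mg, has one instruction per phase. A table per phase would do: hold or continue, grade required for restart, and restart dose, noting any difference during induction. The clinical team decides every entry.
- Reconcile the study-removal sentence in 8.3.1 with 7.3.1 and 7.3.2 by stating whether it means study treatment or the study.
- If no patients remain on treatment, state in the CSR which rule sites applied when reporting interruptions, reductions and dose intensity.

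The cost is wording only: one amendment or clarification letter, or a paragraph in the CSR after checking with sites. No new procedures or patients are needed.

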Particular attention should be given to the follow up of any **Grade 3 or higher** injection site reactions ongoing at the End of Treatment period until resolution, return to baseline, determined to be a stable or chronic condition or until the patient is lost to follow up or the patient has died. Please record the data within EDC per eCRF instructions. In the instance of resolution with sequelae, please be sure to enter the sequelae as a separate AE (eg skin discoloration, persistent induration, scarring “from ISR”). To facilitate this careful follow up, please consider use of video teleconference with the patient during the follow up period post study.

Objective disease assessments will be performed according to RECIST and iRECIST. For Phase 1b, the first assessment will be performed during Cycle 3, at 4 weeks for the nivolumab arm and at 6 weeks for the pembrolizumab arm, and at Weeks 12, 18, and 24, after the first dose of DSP-7888 Dosing Emulsion. After that, objective disease assessments will occur every 12 weeks until patient discontinuation from the study. For Phase 2, patients will be evaluated for objective response to study drug treatment with radiographic imaging every 6 weeks for 24 weeks and then every 12 weeks until progression.

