## 7.3. Withdrawal Criteria

### 7.3.1. Reasons for Discontinuation of Protocol Therapy

Patients have the right to withdraw fully or partially from the study at any time and for any reason without prejudice to their future medical care by the physician or at the institution.

Withdrawal of partial consent means that the patient does not wish to take investigational product any longer but is still willing to collaborate in providing further data by continuing on the study (eg, participate in all subsequent study visits or procedures). Patients may decline to continue receiving investigational product at any time during the study. These patients, as well as those who have stopped receiving investigational product for other reasons (eg, investigator or Sponsor concern) should continue the schedule of study observations. The patients may withdraw consent for continued treatment and still provide consent to be followed up in the follow-up period.

Patients will be discontinued from protocol therapy for any of the following reasons:

- Patients completes 35 cycles (approximately 105 weeks) of study treatment (Phase 2 part only)

Note: if the patient is experiencing clinical benefit, and if, in the opinion of the investigator, it is in the patient's best interest to continue the study beyond 35 cycles, the patient may continue treatment, after documented discussion with the Sponsor

- Documented disease progression (see [Appendix 2](#))
- The need for a prohibited treatment for a concomitant illness or AE
- An AE that precludes further administration of DSP-7888 Dosing Emulsion (see [Section 8.3.1](#) and [Section 8.3.2](#))
- Patient withdraws consent for continued administration of DSP-7888 Dosing Emulsion, nivolumab, or pembrolizumab

Note: if a patient withdraws consent from study treatment, the patient may maintain his/her consent to participate in the follow-up portion of the study

- The investigator believes it is in the patient's best interest to discontinue protocol treatment or to initiate alternative treatment
- Pregnancy
- Lost to follow-up (3 attempts to contact the patient must be made by the investigative site by phone or email before a patient is considered lost to follow-up)
- Patient moves out of the investigator's catchment area or is unable to continue to come to the investigational site
- At Sponsor's request

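### Protocol 8.3.1 takes some Phase 1b patients off the study where 7.3.1 stops only therapy; read literally, follow-up ends early for patients who tolerate DSP-7888 poorly

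*Protocol*

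**What the plan says.** Section 8.3.1 of the protocol (DSP-7888 dose modification, Phase 1b) sets out the steps from 10.5 mg to 3.5 mg to 1.75 mg and closes with: "Patients who experience Grade 3 or higher toxicities with a DSP-7888 Dosing Emulsion dose of 1.75 mg will be removed from the study". The object of the removal is the study, not the study drug.

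The protocol elsewhere keeps the two apart. Section 7.3.1 covers stopping therapy. Its list includes "An AE that precludes further administration of DSP-7888 Dosing Emulsion", with a reference to 8.3.1 and 8.3.2, and it says that "those who have stopped receiving investigational product for other reasons (eg, investigator or Sponsor concern) should continue the schedule of study observations". Section 7.3.2 covers leaving the study. It opens with "Reasons for discontinuation from the study include" and names withdrawal of consent, loss to follow-up, death and a sponsor decision to discontinue the study. It adds: "Patients withdrawing from the study will be requested to complete the same final evaluations as patients completing the study according to this protocol", with emphasis on safety evaluations.

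Two other rules bear on severe toxicity. For a dose-limiting toxicity, Section 6.4 says: "Any patient who experiences a DLT should be permanently removed from study treatment and should not be replaced". For injection site reactions, Section 8.3.5.3 says: "Patients with Grade 3 ISRs that do not require hospitalization may remain on study and receive full dose per investigator's judgment".

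**The concern.** A rule that ends participation because of severe toxicity makes missing data depend on the outcome being measured. The patients concerned have usually already been stepped down from 10.5 mg, since Table 10 reserves 1.75 mg for dose reduction. What could be lost is the course of the triggering event, later immune-related events, remaining scans and survival status.

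Incidence and severity of adverse events are Phase 1b primary endpoints, and SAP version 3.0 makes safety the focus of the final report. A site that follows 8.3.1 and a site that follows 7.3.1 would also handle the same patient differently, so completeness of follow-up would depend on which section was read.

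**Working it through.** No sample size, power or error rate enters this point. The check is a comparison of passages, followed by one piece of date arithmetic on the SAP rules.

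**Step 1. Treatment or participation?**

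| Place | Situation | What ends |
|---|---|---|
| 8.3.1, last sentence | Grade 3 or higher toxicity at 1.75 mg | The study |
| 7.3.1 | Adverse event precluding DSP-7888, citing 8.3.1 | Protocol therapy; observations continue |
| 6.4 | Dose-limiting toxicity | Study treatment |
| 8.3.5.3 | Grade 3 injection site reaction, not hospitalised | Neither, at the investigator's judgment |
| 8.3 and 8.3.1 | Four consecutive DSP-7888 doses missed | DSP-7888; the PD-1 inhibitor may go on alone |
| 8.3.2.1 | Phase 2 patient at 1.75 mg | No removal-from-study rule given |

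The conflict with 7.3.1 is direct, because 7.3.1 cites 8.3.1 as the source of a therapy-only stop and 8.3.1 then orders a study exit. The conflict with 8.3.5.3 is direct for one group: a Phase 1b patient at 1.75 mg with a non-hospitalised Grade 3 reaction falls under both rules. The conflict with 7.3.2 is by omission only. Toxicity is not on that list, but the list is formally open.

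**Step 2. What literal removal would cut.**

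- Tumour assessment: for Phase 1b, the synopsis and 6.1.4.5 run scans until the patient leaves the study, so a study exit stops them. Section 6.1.4.5 also provides disease follow-up after treatment stops without iCPD, for up to 24 months after the last dose.
- Survival: Tables 7 and 8 schedule contacts every 3 months after the date off treatment.
- Adverse events: these are recorded to 30 days after the last dose and followed until resolved, back to baseline, or stable. Section 6.1.4.5 adds: "Particular attention should be given to the follow up of any" Grade 3 or higher injection site reaction still ongoing at the end of treatment. That section is numbered under Phase 2, but it cites Tables 7 and 8 and describes the Phase 1b scan schedule.

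**Step 3. Effect through the SAP.** Section 5.4.1 ends an ongoing injection site reaction at the earliest of data cutoff, end of study, death, last date known alive, and end of treatment + 30 days. Write T for the end-of-treatment date and take a reaction that would still be ongoing at analysis, with death and data cutoff later.

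- Patient kept under observation: truncated no later than T + 30.
- Patient whose study exit is dated T: truncated at T.
- Largest shortening: (T + 30) − T = 30 days.

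If continued follow-up would have recorded an actual end date, the shortening is instead the interval from study exit to that date, for which the documents give no bound. Time to first reaction, and to first Grade 3 or higher reaction, is censored by a similar minimum. Those measures change only for a patient who has not had the event by the time of removal; a patient removed because of such a reaction has already had it.

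**Step 4. Number of patients.** The documents do not report how many patients reached 1.75 mg or had Grade 3 or higher toxicity there. No count or percentage can be derived.

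**The case against.** The strongest reply is that the protocol supplies its own reading. Section 7.3.1 points to 8.3.1 as a reason for stopping therapy, so the last sentence of 8.3.1 may be loose wording for removal from treatment. Nothing in the 30-day recording period, the follow-up of events to resolution, or the reporting of related serious events at any later time exempts these patients, and 7.3.2 still requests final safety evaluations. This stands as far as it goes. It means that loss of follow-up is the literal result, not a certain one. It does not remove the contradiction, since a site has to choose between two instructions.

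Several stronger inferences are tempting and are not supported:

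- **The whole 30-day adverse event window is lost.** The final evaluations in 7.3.2 count against this.
- **A primary endpoint is understated through event duration.** The primary endpoints are incidence and severity, not duration. The triggering event must already be recorded and graded for the rule to apply, and SAP 5.4.1 says only that reaction duration may be analysed.
- **PFS and OS are biased by informative censoring.** SAP version 3.0 (Sections 5 and 5.5) leaves efficacy analyses out of the final report, and its efficacy listings do not include PFS or OS.
- **A fixed share of the safety data is lost.** Any percentage would rest on an assumed count, and losing late follow-up is not losing all of a patient's data.
- **Unrelated toxicity clearly triggers removal.** The sentence carries no such limit, but it closes a sequence that opens with toxicity related to DSP-7888. The text is unclear on this.

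It is also fair that the PD-1-alone provision has a different trigger (four missed treatments) and that 8.3.5.3 overlaps only in part. Both are matters to reconcile rather than direct contradictions throughout.

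**Conclusion.** The point holds as an internal contradiction about whether toxicity at 1.75 mg ends treatment or ends participation. It is direct against 7.3.1, direct against 8.3.5.3 for non-hospitalised Grade 3 reactions, inconsistent with the wording in 6.4, and by omission against 7.3.2.

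Its size is modest and cannot be put as a number of patients. The dose-search part is complete, but 8.3.1 governs all of Phase 1b, so the 10-patient enrichment cohort is covered. The effect that matters for the final report is on safety: follow-up of severe events after the final evaluations, and recorded injection site reaction times. This rests on 8.3.1 being applied as written and on the end-of-study date being set at removal. It should be corrected because it is a stated rule that makes data loss depend on toxicity and is cheap to put right.

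**What to change.** Reword the last sentence of 8.3.1 so that it does not by itself end study participation. Unless a reason in 7.3.2 applies, these patients would continue the follow-up the protocol already sets for patients who stop treatment:

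- adverse events to 30 days after the last study drug, and to resolution, baseline or stability;
- Grade 3 or higher injection site reactions as in 6.1.4.5;
- disease follow-up as in 6.1.4.5 within its stated limits, including the 24-month limit;
- survival contacts as in Tables 7 and 8.

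The sponsor should confirm how the 6.1.4.5 disease follow-up applies to Phase 1b, because Tables 7 and 8 have a survival follow-up column but none for disease assessment after treatment.

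Separately, the sponsor must reconcile the treatment consequence in 8.3.1, and whether it is limited to toxicity related to DSP-7888, with 8.3.5.3 and with the provision for continuing the PD-1 inhibitor alone. No clinical rule is proposed here.

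The cost is one sentence in a protocol amendment and the clarification above. Whether it adds visits depends on that clarification, so it should not be described as free of extra assessments.
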